4.2.7 TRT in ES SCLC

A randomized phase III trial showed that TRT improves PFS in ES SCLC (HR 0.73, p=0.001), and the PFS curves split immediately after administering TRT. The study did not, however, meet the primary endpoint of improved 1-year survival in the overall population (33% vs. 28%, p=0.066), but there was a significant benefit in terms of 18-months (16% vs 9%, p=0.03) and 24-months survival (13% vs. 3%, p=0.004). Among patients with residual thoracic disease after chemotherapy, there was a significant improvement in OS (HR 0.004). Thus, the role of TRT has been debated, and is not routinely offered in Scandinavia, and was not allowed in the CASPIAN or Impower 133.

[figure not shown]

Figure 3 Progression free survival and overall survival curves from the trial of TRT in ES SCLC (CREST).

4.2.8 Synergistic effect of combining RT and immunotherapy

RT has traditionally been considered to be a local treatment, mainly affecting the targeted tumor cells. There are reports of an abscopal effect, i.e. treatment response on lesions outside the RT fields, but these reports are few in numbers.⁴⁹

There are, however, reasons to believe that there is a synergistic effect of concurrent RT and immune checkpoint inhibitor therapy that are of more clinical relevance. In addition to the direct cytotoxic effect on tumor cells, RT may also change the tumor microenvironment in a way that may promote an improved systemic effect of checkpoint inhibitors. It has been shown that RT induce upregulation of tumor surface MHC-I and PD-L1 expression, increase the proportion of beneficial TILs and their effector activity, drive polyclonal T-cell responses, which may create a suitable neoantigen repertoire. On the other hand, RT may also attract immunosuppressive cells. 50-54

Though there are reasons to believe that combining RT and immunotherapy improves efficacy of the systemic treatment, it is not yet established how to optimally combine these therapies. It appears that concurrent administration or administration of immunotherapy immediately after RT is the most effective approach.^{27,52}

Combining immunotherapy and RT in lung cancer, including ES SCLC, appears to be safe,^{55,56} but even if there is a lot of interest in investigating the potential synergistic effect, there is hitherto no results from randomized trials confirming that the combination results in a clinically relevant improved effect. In a recent publication, patients with head and neck squamous cell carcinomas randomized to receive stereotactic body RT to one lesion, did not experience a higher effect of concurrent nivolumab treatment. However, the study was small (n=62), and the results are not necessarily applicable to ES SCLC.⁵⁷

4.2.9 Prophylactic cranial irradiation in ES SCLC

Whether PCI is beneficial for patients who receive combined immunotherapy and chemotherapy is unknown. It is unknown whether receiving checkpoint inhibitor therapy increases the potential detrimental cognitive effect of PCI, and the benefit of PCI may be reduced due to improved disease control due to the improved efficacy of the triple combination.

The only available data on PCI in patients receiving ICI, are from a subgroup analysis of the 44 patients who received PCI as part of the Impower 133 trial. There were no indications of more side effects among those who received PD-L1 inhibitor therapy, but the cohort was small and follow-up did not include assessment of long-term neurocognitive decline.⁵⁸

4.3 Research hypotheses

The main hypothesis is that adding TRT to chemotherapy plus durvalumab provides a survival benefit for patients with extensive stage (ES) small-cell lung cancer (SCLC). Specifically, we hypothesize that:

- combining TRT, chemotherapy and durvalumab is feasible and well tolerated
- adding TRT improves 1- and 2-year survival, median OS, response rates, and PFS
- the patients who benefit the most from the study treatment can be identified through analyses of tissue, blood and stool samples
- PCI is well tolerated, reduces the risk of brain metastases and prolongs survival in ES SCLC patients who
 receive chemotherapy plus durvalumab compared with patients who do not receive PCI

4.4 Rationale for conducting this study

- Chemotherapy plus an PD-L1 inhibitor is considered a new standard of care for first-line treatment of ES SCLC but is not yet available/reimbursed in all countries. Durvalumab plus platinum/etoposide is one of these new standard regimens. However, the survival benefit is limited, especially for the first 6 months, and a more effective treatment is needed.
- A more effective initial therapy might improve survival the first 6 months and long-term survival.
- It has been demonstrated that TRT improves survival in ES SCLC, and the effect in terms of PFS is immediate.
- Several studies suggest a synergistic effect of combining RT and ICI. Concurrent administration appears to be the most effective approach, and we will administer the TRT between the second and third chemoimmunotherapy courses. This is deemed to be the earliest time point that TRT may be administered at all sites. We know that SCLC patients may achieve a substantial response to one chemotherapy course (*Halvorsen*, 2016) and believe that administering TRT earlier than in the CREST trial will make it easier to locate the target lesions, increases the likelihood of irradiating viable tumor cells, and consequently increase the chance for achieving a synergistic effect of the TRT and the immunotherapy and not merely an additive effect.
- Combining high-dose TRT, platinum doublet chemotherapy and ICI appears to be well tolerated. Thus, combining medium dose TRT with durvalumab and carboplatin/etoposide should be feasible and well tolerated. However, since there is no data on this combination, investigating whether ading TRT increases the frequency or severity of side effects is an essential part of this trial.
- The benefits and tolerability of PCI in ES SCLC patients receiving chemotherapy plus ICI are unknown.
 We will compare the timing and frequency of brain metastases between patients who receive PCI and those who do not. Furthermore, we will measure and compare cognitive function before and after PCI.
- The survival benefit from adding ICI does not appear before after 6 months. Thus, we restrict the protocol for patients in performance status 0-1. In a previous trial on chemotherapy in ES SCLC, median OS was below 6 months among patients with a PS of 2 or more.
- The optimal length of durvalumab treatment remains to be defined since there is limited data on the long-term benefit of checkpoint inhibitors in ES SCLC. Thus, durvalumab treatment will continue until PD and need for other treatment, unacceptable toxicity or patients wish to discontinue.
- There is very limited knowledge of prognostic and predictive biomarkers in SCLC in general and for ICI therapy specifically since few have conducted such research and the markers established for other

types of cancer appears to be of little relevance in SCLC. We will collect tumor, blood and stool for translational research aiming at characterizing patients who benefit the most from the study therapy.

SCLC patients with paraneoplastic neurological syndrome (PNS) syndrome and asymptomatic patients
with autoantibodies against neuronal proteins may have a better and more prolonged response to ICIs.
We will investigate whether there are associations between the presence and type of autoantibodies
and long-term benefit of the study therapy.

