- Four courses of durvalumab 1500 mg IV day 1, carboplatin (AUC=5, Calvert's formula) IV day 1 and etoposide 100 mg/m² BSA IV day 1. On days 2-4, etoposide is administered in a dose of 100 mg/m² BSA IV or 200 mg/m² BSA PO. Chemoimmunotherapy courses are administered every three weeks. After completing four courses, durvalumab 1500 mg IV is given every four weeks until intolerable toxicity, patient's wish, or disease progression and need for other treatment.
- The dose of durvalumab will be adjusted to 20 mg/kg if a patient's body weight falls below 30 kg
- Patients randomized to the experimental arm will receive TRT of 30 Gy in 10 fractions, one fraction per day, 5 fractions per week, between the second and third chemo-immunotherapy course.
- Patients who achieve a response when evaluated after completion of chemo-immunotherapy may be offered PCI of 25 Gy in 10 fractions or 30 Gy in 15 fractions, one fraction per day, 5 fractions per week according to local treatment policy.

Safety assessments:

Toxicity will be classified according to CTCAE v5.0. Cognitive function will be assessed using the MoCA test. Patients will report HRQoL on the EORTC QLQ C30+LC13.

Efficacy assessments:

OS will be measured from the day of randomization until death by any cause, PFS from the day of randomization until RECIST 1.1 progression or death by any cause. Response to treatment and progression will be assessed according to RECIST 1.1. Response to treatment and progression will be assessed on CT and MRI scans at regular intervals. Sensitivity analyses including measurement of previously irradiated lesions (both thoracic lesions and brain metastases) will be performed.

Statistical methods and data analysis:

Cox proportional hazard method will be used to compare survival. The primary survival analyses will be performed 14 months after the last patient entry (to ensure that 1-year survival data are captured). Pearson's Chi-Square test will be used to compare toxicity, overall response rates, and treatment completion rates. Mann-Whitney's test will be used to compare number of completed chemo-immunotherapy- and durvalumab-courses.

Median OS will be estimated using the Kaplan-Meier method, and a Cox-model will be used for multivariable survival analysis adjusting for established prognostic factors in the target population (sex, PS, disease stage, presence brain metastases and liver metastases) and age. A separate analysis plan will be defined for the biomarker analyses.

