8.4 Prophylactic cranial irradiation (PCI)

PCI is not mandatory, but patients who respond to chemoimmunotherapy and have not previously received brain irradiation, should be offered PCI at the hospitals where this is established treatment of ES SCLC.

PCI should start between 4 to 6 weeks after the last chemoimmunotherapy course. PCI should be administered according to local routines. Hippocampus-sparing PCI is allowed. Recommended schedules are 25 Gy in 10 fractions or 30 Gy in 15 fractions. One schedule should be used for all patients at each site. PCI may be administered concurrently with durvalumab infusions.

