14.3.3 Exploratory analyses

Cognitive function (MoCA-scores) will be compared using the Mann-Whitney test, and time until decline of MoCA-scores will be compared. Associations between biomarkers in tissue, blood and stool samples, and treatment outcomes, baseline characteristics, and survival will be investigated. A detailed project plan including biomarker and data analysis plan will be defined when sufficient biological material and clinical data to start the translational research have been collected.

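### Grouping patients by PCI received will favour PCI on survival and time to brain metastasis, if time runs from randomisation, even when PCI has no effect

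*Protocol*

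**What the plan says.** **The contrast.** Section 4.4 says: "We will compare the timing and frequency of brain metastases between patients who receive PCI and those who do not". Section 4.3 hypothesises that "PCI is well tolerated, reduces the risk of brain metastases and prolongs survival"; the comparator there is everyone who goes without it. Section 14.1 lists, as an exploratory endpoint, cognition in PCI recipients against non-recipients, and Section 14.3.3 adds: "Cognitive function (MoCA-scores) will be compared using the Mann-Whitney test".

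**Who can receive PCI.** Section 8.4: "patients who respond to chemoimmunotherapy and have not previously received brain irradiation, should be offered PCI at the hospitals where this is established treatment". The Synopsis also makes response the gateway: "Patients who achieve a response when evaluated after completion of chemo-immunotherapy may be offered PCI". On timing, Section 8.4 says: "PCI should start between 4 to 6 weeks after the last chemoimmunotherapy course". Course 4 is at week 9 in the Section 2 schedule, so PCI starts at week 9 + 4 to 9 + 6, which is week 13 to 15, as the schedule shows.

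**Time origin and methods.** The Synopsis counts OS and PFS from randomisation. Section 14.3.2 names Pearson's chi-square for the frequency of brain metastases, Kaplan-Meier for time to brain progression, and a multivariable Cox model with sex, performance status, stage, brain metastases, liver metastases and age. Response is not in that list.

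**A separate objective.** The brain-metastasis objective in the Synopsis compares the randomised arms, not PCI groups.

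**The concern.** PCI received is decided after randomisation, by events that are themselves prognostic. As worded, the no-PCI group holds everyone who dies before week 13 to 15, every non-responder, every patient whose brain was already irradiated, and responders at hospitals that do not use PCI. The PCI group holds only responders who have survived about three months. Two biases follow: immortal time (PCI patients cannot die before PCI) and selection on response.

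Section 4.2.9 says the benefit of PCI with chemo-immunotherapy is unknown, and that the only available data come from a subgroup of 44 patients. A PCI result from a trial of 302 could therefore carry weight. A comparison that favours PCI whether or not it works cannot test the hypothesis in Section 4.3.

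**Working it through.** **1. Check of the survival inputs.** The protocol gives no figure for the PCI comparison, so only the inputs reused here can be checked against it (Section 14.4).

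- Exponential survival with medians 13.10 and 20.02 months gives 12-month survival of 53.0% and 66.0%, as stated.
- With 30 months' accrual and 14 months' further follow-up, the mean event probability is 0.689. Freedman's formula at HR 0.65 needs 175 events: 175 / 0.689 = 254 patients, or 127 per arm (stated: 128).
- 256 / 0.85 = 301.2, rounded up to 302, as stated.

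**2. Deaths before PCI can start.** The control hazard is ln 2 / 13.10 = 0.0529 per month. Weeks 13 and 15 are 2.99 and 3.45 months. Deaths by then are 1 - exp(-0.0529 × 2.99) = 14.6% and 1 - exp(-0.0529 × 3.45) = 16.7%. All count as no PCI.

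**3. Immortal time alone, by hand.** PCI has no effect and response is not prognostic. Take PCI at week 14 (3.22 months), 65% responders (the figure in Section 4.1.2), and three assumptions: 15% baseline brain metastases, 25% 12-month brain-metastasis risk (hazard 0.0240 per month) and 50% uptake among the eligible.

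- Share receiving PCI: 0.65 × 0.85 × 0.843 (alive) × 0.926 (no new brain metastasis) × 0.5 = 0.216, about 65 of 302.
- 1-year OS with PCI: exp(-0.0529 × (12 - 3.22)) = 62.8%.
- 1-year OS without PCI: (0.530 - 0.216 × 0.628) / (1 - 0.216) = 50.3%.

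That is a gap of about 12 points with no PCI effect.

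**4. Simulation with no PCI effect.** It uses the control median, 65% responders, and PCI at week 13-15 only for responders without baseline brain metastases who are alive and free of brain metastases. Assumed, because the protocol gives no values: uptake 30-90%; responder death HR 1.0, 0.5 or 0.3; 12-month brain-metastasis risk 25-40%; responder brain-metastasis hazard ratio 0.5-1.0; baseline brain metastases 10-20%. Ratios and frequencies come from 400,000 patients per scenario. False-positive rates come from 400 trials of 302 patients, at 30-50% uptake only.

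| Comparison from randomisation | Ratio, PCI / no PCI | Falsely significant for PCI |
|---|---|---|
| OS, response not prognostic | 0.70-0.79 | 22-38% |
| OS, responder HR 0.5 | 0.48-0.61 | 63-94% |
| OS, responder HR 0.3 | 0.35-0.40 | not run |
| Time to brain metastasis, all scenarios | 0.53-0.75 | 10-26% |

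The last false-positive range covers 25% 12-month brain-metastasis risk and responder death HR 1.0 or 0.5.

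**5. Crude frequency of brain metastasis.** With no PCI effect, the percentages with and without PCI are:

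- response not prognostic: 25.9 vs 27.4;
- responder death HR 0.5: 28.9 vs 26.6;
- responder death HR 0.3: 31.2 vs 23.8;
- responder death HR 0.5, 40% 12-month risk, and half the brain-metastasis hazard in responders: 26.3 vs 30.6;
- responder death HR 0.5, with baseline brain metastases counted in the no-PCI group: 28.9 vs 40.7.

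The sign changes because PCI patients live longer and have more time at risk.

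**6. The same data with the set restricted.** Among responders alive and free of brain metastases at week 15, with time from week 15, the OS ratio is 0.99-1.01 and the brain-metastasis ratio 0.98-1.01. A week-15 landmark without restriction to responders leaves the OS HR at 0.74-0.78 when the responder HR is 0.5. Both parts are needed.

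**The case against.** The strongest defence is that this is exploratory and partly the business of an analysis plan that is not shown. The main sentence is in a rationale section. Section 14.3.2 does not tie chi-square or Kaplan-Meier to PCI groups, and no time origin is given for brain metastasis by PCI. A landmark or time-dependent analysis could still be specified elsewhere. On cognition, Section 4.4 also plans measurement before and after PCI, and a MoCA at week 11-12 precedes PCI.

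Most of that is right, and it limits the point. What remains is wording the protocol itself fixes: received against not received, in Sections 4.3, 4.4 and 14.1. None of the named methods repairs that contrast; the Cox model adjusts for several prognostic factors but not for response.

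Stronger readings are tempting, and the protocol does not support them:

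- *Every PCI comparison will look beneficial.* Crude frequency can go either way, and nothing in the protocol lets one compute a direction for MoCA.
- *A survival test by PCI is planned.* Survival by PCI appears only as a hypothesis in Section 4.3. No objective, endpoint or test states it, and the Synopsis version of that hypothesis concerns toxicity only.
- *The trial's main results are compromised.* The primary endpoint and the brain-metastasis objective compare randomised arms.
- *The missing landmark is itself an omission.* That detail may properly sit in an analysis plan. The fault is the grouping.

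**Conclusion.** The point holds in a limited form. Comparing patients by PCI received, with time from randomisation, favours PCI on survival and on time to brain metastasis in every no-effect scenario run. Crude brain-metastasis frequency is biased in an unpredictable direction, so it cannot be interpreted either.

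The sizes rest on assumed uptake, responder prognosis and brain-metastasis risk, and should be read as ranges. The direction for survival needs much less: deaths before week 13 to 15 can fall only in the no-PCI group. The null result after restriction assumes that uptake among eligible patients is unrelated to prognosis, so it shows that the two structural biases are removed, not that all confounding is. The matter is confined to exploratory and hypothesis-level comparisons and is a cheap improvement.

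**What to change.** Reword the PCI comparisons in Sections 4.3, 4.4 and 14.1, and carry the following into the analysis:

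- **Set.** Include only patients who, at the evaluation after chemo-immunotherapy, are alive, responding, free of brain metastases and without earlier brain irradiation. CT and brain MRI are already scheduled at week 11-12.
- **Time.** Start at a landmark that allows for delayed courses, or treat PCI as a time-dependent covariate within this set. Section 8.2.5 lets a course slip by up to three weeks; one such delay moves PCI from week 13-15 to week 16-18, so a fixed week-15 landmark would misclassify some patients.
- **Adjustment.** Include randomised arm and the prognostic factors listed in Section 14.3.2.
- **Brain metastasis.** Treat death as a competing event.
- **MoCA.** Compare scores adjusted for the pre-PCI score at week 11-12.
- **Reporting.** Label all PCI results non-randomised.

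This changes analysis wording only; it needs no new data and leaves PCI practice alone. The cost is a smaller comparison set and wider intervals.

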7.3 Withdrawal of patients from study treatment and/or study

7.3.1 Permanent discontinuation of chemotherapy and durvalumab

Discontinuation of study treatment, for any reason, does not impact the patient's participation in the study. A patient who decides to discontinue IP should be asked about the reason(s) for discontinuation and the presence of any AE. The patient should continue attending subsequent study visits, and data collection should continue according to the study protocol. If the patient does not agree to continue in-person study visits, a modified follow-up must be arranged to ensure the collection of endpoints and safety information. This follow-up could be a telephone contact with the patient, a contact with a relative or treating physician, or information from medical records. The approach taken should be recorded in the medical records. A patient who agrees to modified follow-up is not considered to have withdrawn consent or to have withdrawn from the study.

Patients who permanently discontinue study treatment for other reasons than objective RECIST disease progression should be followed according to the study schedule similar to patients who are on study treatment.

All patients will be followed for survival until the end of the study. Patients who decline to return to the site for evaluations should be contacted by telephone if they agree.

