8.2.6 Duration of treatment and criteria for treatment through progression and for retreatment

Maximum 4 courses of chemoimmunotherapy will be administered. Durvalumab treatment will then continue until PD and need for other treatment, unacceptable toxicity or patients wish to discontinue.

Chemotherapy should be discontinued if a course is postponed more than three weeks, and may be discontinued earlier if severe, unacceptable, toxicity considered to be due to the chemotherapy occurs. Patients may continue durvalumab regardless of the number of chemotherapy courses completed provided the criteria for discontinuation of durvalumab are not met.

Chemo- and/or immunotherapy will be discontinued if RECIST 1.1-defined radiological progression and need for other treatment occur. Other reasons for discontinuation include unacceptable toxicity, withdrawal of consent, or patient's wish.

During the treatment period, patients who are clinically stable at an initial RECIST 1.1-defined PD may continue to receive study treatment at the discretion of the Investigator and patient as long as they are deemed to be receiving clinical benefit. In case, a follow-up scan is to be collected after the initial RECIST 1.1-defined PD, 4-6 weeks after the prior assessment of PD for confirmation of PD and to ensure that potentially rapid progression of relapsing SCLC is revealed within a reasonable timeframe to ensure that patients may be offered other treatment for PD.

Patients with PD who continue to receive IP at the discretion of the Investigator should undergo image acquisitions and tumor assessments according to the regular schedule for the duration of treatment.

Patients with rapid tumor progression or with symptomatic progression that requires urgent medical intervention (e.g. CNS-metastasis, respiratory failure due to tumor compression, or spinal cord compression) will usually not be eligible for continuing durvalumab treatment. If a general disease control has been achieved, and oligometastatic progression occurs, exceptions may be considered after discussing with the Chief Investigator.

For all patients who are treated through progression and for patients who are restarting

durvalumab (alone or in combination with chemotherapy), the Investigator should ensure that:

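### The number of durvalumab courses mainly reflects disease control, so the planned Mann-Whitney test on it says little about whether durvalumab is tolerated and deliverable after TRT

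*Protocol*

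**What the plan says.** The statistical methods paragraph of the protocol synopsis (section 1) states: "Mann-Whitney's test will be used to compare number of completed chemo-immunotherapy- and durvalumab-courses". The sentence before it reads: "Pearson's Chi-Square test will be used to compare toxicity, overall response rates, and treatment completion rates".

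The two kinds of course differ. For the first, section 8.2.6 sets a ceiling: "Maximum 4 courses of chemoimmunotherapy will be administered". For durvalumab there is none; section 4.4 says: "Thus, durvalumab treatment will continue until PD and need for other treatment, unacceptable toxicity or patients wish to discontinue". Sections 8.1.1 and 8.2.6 give the same rule.

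Section 4.3 holds two hypotheses that bear on this count. One is that "combining TRT, chemotherapy and durvalumab is feasible and well tolerated". The other is that "adding TRT improves 1- and 2-year survival, median OS, response rates, and PFS".

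The protocol gives the durvalumab count no time window, no split by reason for stopping and no handling of patients still on treatment. On data capture, section 7.3.1 says that a patient who stops "should be asked about the reason(s) for discontinuation and the presence of any AE". Section 13.6 lists the action taken with study treatment as a variable for SAEs; for other AEs it lists only a description and the maximum grade.

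**The concern.** A patient who stops durvalumab for pneumonitis after six courses and one who stops for progression after six courses get the same score. If TRT delays progression, as the protocol expects, patients stay on durvalumab longer and the count rises, whatever happens to tolerability. Extra stopping for toxicity pulls the count down, and the two effects offset each other.

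At stake is a secondary message of the trial. An equal or higher number of courses in the TRT arm could be reported as reassurance about giving durvalumab after TRT when more patients had in fact stopped for toxicity. Section 4.4 says there are no data on this combination and treats the study of side effects as essential, so the measure should be able to show such an excess.

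**Working it through.** **The plan's own figures.** The protocol gives no power or effect size for the course count. Its sample size does reproduce. A hazard ratio of 0.65 needs 175 events (Freedman). With 30 months' accrual and 14 months' further follow-up, event probabilities are 0.761 and 0.615, mean 0.688. Then 175 / 0.688 = 254.4, or 127.2 per arm against the stated 128. Inflation gives 256 / 0.85 = 301.2, hence 302, or 151 per arm.

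**Inputs**
- Control median time to a progression stop: 5.2 months, the median PFS with chemotherapy plus atezolizumab quoted in section 4.2.4.
- Effect of TRT on progression: section 4.2.7 reports that "TRT improves PFS in ES SCLC (HR 0.73, p=0.001".
- Control patients stopping for toxicity: 9.4%, the durvalumab monotherapy figure in section 4.5.2.
- Toxicity-stop hazard under TRT: doubled. This is an assumption; the protocol gives no figure.

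**Closed form** (exponential times, full follow-up)
- Control progression hazard: ln 2 / 5.2 = 0.1333 per month.
- Control toxicity hazard: 0.1333 × 0.094 / 0.906 = 0.01383.
- Control mean time on durvalumab: 1 / (0.1333 + 0.01383) = 6.8 months.
- TRT hazards: 0.73 × 0.1333 = 0.0973 and 2 × 0.01383 = 0.0277, total 0.1250.
- TRT mean time on durvalumab: 1 / 0.1250 = 8.0 months. Share stopping for toxicity: 0.0277 / 0.1250 = 22%.
- Break-even multiplier m, from 0.73 × 0.1333 + m × 0.01383 = 0.1333 + 0.01383: m = 1 + 0.27 × 0.906 / 0.094 = 3.6. At a hazard ratio of 0.65, m = 1 + 0.35 × 0.906 / 0.094 = 4.4.

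Mean time on durvalumab thus falls below control only if TRT raises the toxicity-stop hazard more than 3.6-fold.

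**Simulation** (151 per arm; follow-up uniform on 14 to 44 months, since 14 + 30 = 44; courses at weeks 0, 3, 6, 9, 13, then every 4 weeks). The ranges cover several independent runs.

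| PFS HR | Toxicity-stop hazard | Toxicity stops, control vs TRT | Mean courses, control vs TRT | Mann-Whitney significantly more / fewer under TRT | Cause-specific log-rank detects excess |
|---|---|---|---|---|---|
| 0.73 | ×2 | 9% vs 21% | 8.3–8.4 vs 9.4–9.5 | 22–24% / 0–0.1% | about 60% |
| 0.73 | ×3 | 9% vs 29% | 8.4 vs 8.7 | not tabulated / 0.4% | 97% |
| 0.65 | ×2 | 9.5% vs 24.2%* | 8.5 vs 10.7* | 43–46% / 0% | not tabulated |
| 0.85 | ×2 | not tabulated | not tabulated | 4–5% / 1–1.5% | not tabulated |
| 1.0 | ×2 | 9.4% vs 17.2%* | 8.5 vs 7.9* | under 1% / 8–11% | 54% |

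*Full follow-up.

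With no added toxicity the cause-specific test rejects in about 2.5% of trials, its nominal one-sided level. With control medians of 4.3 to 7 months and control toxicity stops of 5% to 15%, at hazard ratio 0.73 and a doubled hazard, Mann-Whitney shows significantly fewer courses in under 1% of trials and the cause-specific test detects the excess in 33% to 80%.

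**Why not a plain proportion.** The crude share stopping for toxicity rises with time on treatment. At hazard ratio 0.73 and no added toxicity it is 0.01383 / (0.0973 + 0.01383) = 12.4% against 9.4%. The cause-specific comparison does not have this bias.

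**The case against.** The strongest reply is that the protocol never makes this count its test of feasibility. It appears in one synopsis sentence, is not a listed endpoint, is not repeated in section 14.3 and carries no decision rule. As a record of drug delivered it is correct: in the scenario above TRT patients do receive more durvalumab. Tolerability is examined elsewhere, through AE frequency and severity (14.3.1), quality of life with dyspnea as a primary scale (14.3.2) and committee review of SAEs (6.2). Delivery of the chemo-immunotherapy phase has the capped count and completion rates. All of this stands. A reader might infer that the trial cannot answer its delivery question, or that excess pneumonitis would go unseen. The documents support neither.

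Three further inferences should be resisted:
- That the count necessarily reverses. This needs a clear PFS effect. The 0.73 comes from a trial of TRT without immunotherapy, and the model applies it from time zero although TRT starts at weeks 3 to 4.
- That counts are cut off at the 14-month analysis. That date belongs to the survival analysis; none is set for the course count.
- That toxicity stops cannot be identified. Section 7.3.1 has the reason asked, section 13.9 makes laboratory or vital-sign deterioration that ends treatment reportable as an AE, and the CRF is not shown.

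It can also be said that a split by reason is normal analysis-plan content, and that plan is not at hand. This is fair as to detail. But the protocol itself names the test, and the point concerns that choice.

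**Conclusion.** The point holds in a limited form. A Mann-Whitney test on open-ended durvalumab courses mixes disease control with tolerability and is dominated by the former. Under the protocol's quoted background figures and an assumed doubling of the toxicity-stop hazard, toxicity stops go from about 9% to 21% while the TRT arm gets about one course more on average. Where TRT has little or no effect on PFS the test rarely misleads significantly, but it is weak: it shows significantly fewer courses in about 1% to 11% of trials at the 9.4% control rate.

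The sizes rest on exponential times, rates borrowed from other trials, an assumed toxicity multiplier, and PFS standing in for time to stopping, although stopping also requires need for other treatment and treatment beyond progression is allowed. The mechanism does not depend on these choices. The primary survival analysis is unaffected. The AE comparisons do not share the problem, and the count capped at four courses is much less exposed to it.

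**What to change.** - Keep the number of durvalumab courses as a descriptive exposure summary by arm, without a test.
- In place of the Mann-Whitney test on durvalumab courses, compare time to stopping durvalumab for toxicity between arms by a cause-specific log-rank test or Cox model. Treat progression, death and patient's wish as competing events, censor patients still on treatment, and show cumulative incidence curves by reason.
- Use stopping for toxicity or patient's wish as a sensitivity analysis only. If wish stops are equally frequent in both arms (assumed at 5% to 15% of controls), power for the composite falls to roughly 32% to 44%.
- Record the reason for stopping, which section 7.3.1 already has asked, as a coded and dated CRF field for every patient.

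The cost is analysis wording, slightly more analysis and one CRF field. No patients, procedures or treatment rules change. The new comparison has only about 60% power for a doubled toxicity-stop hazard under the base assumptions, so a non-significant result should not be read as proof of tolerability.
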